9.0 Study Treatment Exposure and Compliance

The duration of exposure to venetoclax/placebo will be summarized by treatment arm, for safety analysis set as described in Section 5.1. Duration of exposure is defined for each subject as (last dose date – first dose date) + 1. Duration of exposure will be summarized using the following statistics (months): sample size (N), mean, standard deviation, median, and range. In addition, the number and percentage of subjects exposed to venetoclax/placebo will be summarized for the following categories of exposure duration:

- 0 to 4 weeks (0 to 28 days),
- > 4 weeks to 8 weeks (28 to 56 days),
- > 8 weeks to 12 weeks (57 to 84 days),
- > 12 weeks to 16 weeks (85 to 112 days),
- > 16 weeks to 20 weeks (113 to 140 days),
- > 20 weeks to 24 weeks (141 to 168 days),
- > 24 weeks to 28 weeks (169 to 196 days),
- > 28 weeks to 32 weeks (197 to 224 days),
- > 32 weeks to 36 weeks (225 to 252 days),

- > 36 weeks to 52 weeks (253 to 364 days),
- > 52 weeks (> 364 days).

The number of cycles that subjects are exposed to study drug will be summarized by treatment arm. There will be no statistical comparison for the study treatment exposure between the two treatment arms.

10.0 Efficacy Analysis

10.1 General Considerations

Unless otherwise noted, for all statistical analysis, statistical significance will be determined by a two-sided P value ≤ 0.05 (when rounded to three decimal places).

When the 133st death in the full analysis set occurs, there will be a final review of the eCRF data. After the data collection is completed and reviewed for completeness and all data management quality assurance (QA) and quality control (QC) procedures are performed, the study blind will be broken and clinical database data will be extracted for documentation and statistical analyses of the efficacy and safety data. Efficacy analyses will be performed on the full analysis set.

Unless otherwise specified, the primary analysis of all response/progression related endpoints (e.g., CR/CRi) will be based on the investigator assessment. Sensitivity analyses will be performed based on Independent Review Committee's assessment.

For the analysis of all response/progression related endpoints, MRD response rate, and transfusion independence rate, the data collected after the data cutoff date or initiation of post treatment therapy, whichever comes earlier, will be excluded.

Censoring Dates for Prematurely Blind Broken Subjects

For all efficacy endpoints except OS, if the subject's blind has prematurely broken by sites before "Cutoff" date, the date of premature blind break will be set as "Cutoff" date for the subject.

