EFS will be defined as the number of days from randomization to the date of progressive disease, relapse from CR to CRi, treatment failure defined as failure to achieve CR, CRi, PR, or MFLS, or death from any cause. If a specified event does not occur, subjects will be censored at the date of last disease assessment. Data for subjects without any disease assessments performed after randomization will be censored at the date of randomization. The distribution of EFS will be estimated for each treatment arm using Kaplan-Meier methodology and compared between treatment arms using the log-rank test stratified by AML status (secondary, de novo) and age ($18 - < 75, \geq 75$).

Post baseline transfusion independence rate will be calculated as the portion of subjects who achieved transfusion independence post baseline. Transfusion independence is defined as a period of at least 56 days with no transfusion between the first dose of study drug and the last dose of study drug plus 30 days. In addition, the rate of conversion will be calculated as proportion of subjects being post-baseline transfusion independent from baseline transfusion dependence. The transfusion independence rate will be evaluated for 1) RBC and 2) platelets. All randomized subjects will be included to estimate the post-baseline transfusion independence rate.

Post baseline transfusion independence rate will be estimated as the proportion of subjects known to achieve transfusion independence during the evaluation period. Transfusion independence rate will be compared between treatment arms using CMH test stratified by AML status (secondary, de novo) and age ($18 - < 75, \geq 75$). In addition, 95% confidence interval will be constructed for transfusion independence rate.

The rates of conversion from baseline transfusion dependence to post-baseline transfusion independence will be estimated. The conversion rate will be evaluated for 1) RBC and 2) platelets.

The proportion of subjects with complete remission or complete remission with partial hematologic recovery (CR + CRh) by the initiation of Cycle 2 will be calculated. CR + CRh rate by the initiation of Cycle 2 will be compared between treatment arms using CMH test stratified by AML status (secondary, de novo) and age ($18 < 75, \geq 75$). In addition, 95% confidence interval will be constructed for CR + CRh rate by the initiation of Cycle 2.

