6.0 Analysis Conventions

General Considerations

Unless otherwise noted, for all statistical analyses, statistical significance will be determined by a two-sided P value ≤ 0.05 . The date of randomization is defined as the date that the IVRS/IWRS issues a randomization number.

Definition of Study Drug

Unless otherwise specified, the study drug in this document refers to venetoclax/placebo and LDAC. The first dose date of study drug is defined as the date the 1st dose of venetoclax/placebo or LDAC, whichever occurs first, is administered. The last dose date of study drug is defined as the date the last dose of venetoclax/placebo or LDAC, whichever occurs later, is administered.

Definition of Baseline

All baseline summary statistics and analyses will be based on characteristics prior to the initiation of any component of study drug (or randomization for non-treated subjects). Unless otherwise stated, baseline for a given variable will be defined as the last value for that variable obtained prior to the first dose of any component of study drug or randomization for non-treated subjects.

Definition of Final Observation

The final observation in [Table 2](#) and [Table 3](#) is defined as the last non-missing observation collected after the first dose of study drug to the last dose of study drug + 30 days.

Definition of Data Cutoff Date

The data cutoff date for interim analysis (IA) will be the projected date of the 100th death occurred in the full analysis set. The data cutoff date for final analysis (FA) will be the projected date of the 133th death occurred in the full analysis set.

The same data cutoff date will be implemented for both efficacy and safety analyses.

Stratification Factor for Efficacy Analyses

AML status (secondary, de novo) and age ($18 < 75, \geq 75$) will be used in all stratified analyses of the efficacy endpoints. The stratification factor value under which the subject is randomized by the IVRS/IWRS will be used in the efficacy analyses.

Definition of Cycle Rx Days in Each Cycle

Cycle Rx Days for each cycle are calculated for each time point relative to first dose of study drug in each cycle. The day of the first dose of study drug in each cycle is defined as Cycle Rx Day 1, while the day prior to the first dose of study drug is defined as Cycle Rx Day -1 (there is no Cycle Rx Day 0).

Definition of Analysis Windows

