10.2 Primary Efficacy Analysis

10.2.1 Overall Survival

Overall survival will be defined as the number of days from the date of randomization to the date of death. All events of death will be included, regardless of whether the event occurred while the subject was still taking study drug, or after the subject discontinued study drug. If a subject has not died, then the data will be censored at the date the subject was last known to be alive on or before the cutoff date. The date of the last known alive will be determined by selecting the last available date of the following study procedures for a subject: start date of adverse event, bone marrow collection, disease assessment, vital signs assessment, clinical laboratory collection, study drug administration, start date of concomitant medicine, transfusion procedure, survival follow-up, biospecimen sample collection, quality of life assessments, and performance status. All subjects in the full analysis set will be included in the analysis.

The distribution of overall survival will be estimated for each treatment arm using Kaplan-Meier methodology and compared between treatment arms using the log-rank test, stratified by AML status (de novo, secondary) and age ($18 - < 75, \geq 75$). The hazard ratio between treatment arms will be estimated using the Cox proportional hazards model, stratified by AML status (de novo, secondary) and age ($18 - < 75, \geq 75$).

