10.3.8 Event-free Survival

Event-free Survival (EFS) will be defined as the number of days from randomization to the date of progressive disease, confirmed morphologic relapse from CR or CRi, treatment failure defined as failure to achieve CR, CRi or MLFS after at least 6 cycles of study treatment collected on study drug completion eCRF or death from any cause. The confirmation is required for morphologic relapse (MR). Based on the IWG criteria implemented in the protocol, if the bone marrow blasts are between 5 - 10%, a repeated bone marrow assessment should be conducted to distinguish between bone marrow regeneration and relapse. For MR with bone marrow blast $\leq 10\%$ and followed by a non-PD/non-MR response prior to start of post-treatment therapy, this MR is considered an unconfirmed MR and therefore, the subject is still considered to be a responder.

If the specified event does not occur, subjects will be censored. The detailed censoring rule is described in [Table 4](#). Data for subjects without any disease assessments performed after randomization will be censored at the time of randomization.

Table 4. Event/Censor and Corresponding Event/Censor Time for EFS

Situation	Event/Censor	Event Time/Censor Time
PD, confirmed morphologic relapse (MR),* and treatment failure events on or prior to any post-treatment therapy and data cutoff date, whichever is earliest	Event	Earliest PD, MR or treatment failure event date
Death event on or prior to data cutoff date regardless whether it occurred after any post-treatment therapy initiated	Event	Death date
No PD, confirmed MR,* treatment failure, or death events, and without post-treatment therapy initiated on or prior to the data cutoff date	Censor	Last disease assessment date (bone marrow or hematology lab collection date) on or prior to the data cutoff date
No confirmed MR,* PD, or treatment failure on or prior to post-treatment therapy initiated on or prior to the data cutoff date, and no death on or prior to data cutoff	Censor	Start date of post-treatment therapy

* An un-confirmed MR is defined as a MR with bone marrow blast $\leq 10\%$ and followed by non-PD/Non-MR prior to the post-treatment therapy. Otherwise, MR is considered to be a confirmed MR.

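### After a site breaks the blind early, a later death in a subject who was still event-free is censored in EFS, although EFS is defined to include death from any cause

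*SAP*

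**What the plan says.** Two SAP rules act together.

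- **SAP 10.1**, on subjects whose blind a site has broken prematurely, applies "For all efficacy endpoints except OS" and states that "the date of premature blind break will be set as" the subject's cutoff. EFS is not exempted.
- **SAP 10.3.8** ends its list of EFS events with "collected on study drug completion eCRF or death from any cause" (the first words of that quote belong to the treatment-failure component). Table 4 then gives the death row as "Death event on or prior to data cutoff date regardless whether it occurred after any post-treatment therapy initiated". For a subject with no event and no new therapy, the censoring date is "Last disease assessment date (bone marrow or hematology lab collection date) on or prior to the data cutoff date".

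Three other places matter for comparison.

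- **SAP 6.0** defines the cutoff at study level: "The data cutoff date for final analysis (FA) will be the projected date of the 133th death occurred in the full analysis set".
- **SAP 10.2.1** keeps every death for OS: "All events of death will be included, regardless of whether the event occurred while the subject was still taking study drug", or after stopping it.
- **Protocol 8.1.4.2** censors EFS only in the absence of an event: "If a specified event does not occur, subjects will be censored at the date of last disease assessment". It has no rule for broken blinds.

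**The concern.** Death is a component of both OS and EFS, but the two endpoints treat it differently after a site unblinding. Knowledge of the assignment can sway an assessed event such as progression or relapse. It does not change whether or when a death is recorded. Table 4 already draws this line for post-treatment therapy: later progression, relapse and treatment failure are set aside, while a later death still counts. The blind-break rule does not draw it.

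At stake is a ranked, alpha-controlled secondary endpoint. If sites unblind subjects whose outlook has changed, the censoring depends on prognosis. If that also happens at different rates in the two arms, the EFS hazard ratio can be biased. No planned analysis would show this. The IRC-based EFS analysis (SAP 10.5) falls under the same rule, and the analyses without a cutoff (SAP 10.6) do not list EFS.

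**Working it through.** **1. Following one subject through the rules.** Take a subject with no progression, relapse or treatment failure whose site breaks the blind at time U, and who dies at time D, after U and before the study cutoff.

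- OS: exempt from the rule, so an event at D.
- EFS: the subject's cutoff becomes U. Since D is later than U, Table 4's death row is not met. The subject is censored at the last disease assessment on or before U, or at the start of post-treatment therapy if that came earlier.
- The same subject with new therapy at time U instead of unblinding: Table 4 counts the death at D as an EFS event.
- Protocol 8.1.4.2: a specified event occurred, so an event at D.

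**2. The plan's own figure, and whether it moves.** Inputs from SAP 4.3: medians of 6 and 11 months (HR 6/11 = 0.545), 2:1 allocation, two-sided alpha 0.05, 90% power, one O'Brien-Fleming interim at 100 of 133 deaths.

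- Schoenfeld, fixed design: (1.960 + 1.282)² / [(2/3)(1/3)(ln 0.545)²] = 10.51 / (0.2222 × 0.367) = 129 deaths.
- With the interim analysis: 131 deaths for 90% power. Power at 133 deaths is 90.4 to 90.5%.
- One-sided boundaries: 0.0097 and 0.0221, against 0.010 and 0.022 in SAP Table 1.

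The 133 deaths are reproduced to within 2. OS is exempt from the blind-break rule, so none of this changes. The documents give no EFS event count, EFS power or expected number of site unblindings, so there is no planned EFS figure to recompute.

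**3. An illustrative count (unblinding rate assumed).** 5% of 210 is about 10 subjects and 10% is 21. The trial-wide death fraction at the final analysis is 133/210 = 0.63. If that fraction of the unblinded subjects died event-free before the cutoff, 10 × 0.63 = 6 and 21 × 0.63 = 13 deaths would not count.

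**4. Illustrative effect on the hazard ratio (all trial-conduct inputs assumed).** Simulation of 140 and 70 subjects, with the OS medians standing in for EFS, 18-month accrual, cutoff at month 24, and unblinding within 2 months before death. Hazard ratios are from a Cox fit, with simulation variation of about 0.01.

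| Unblinded, venetoclax / placebo | Events lost | HR, all deaths counted | HR, current rule |
|---|---|---|---|
| 5% / 5% | about 7 | 0.55 | 0.55 |
| 10% / 10% | about 14 | 0.55 | 0.55 |
| 2% / 10% | about 7 | 0.55 | 0.59 |
| 5% / 20% | about 15 | 0.55 | 0.64 |
| 10% / 2% | about 9 | 0.55 | 0.51 |

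A one-step log-rank estimate sits lower throughout (0.50 with all deaths counted; 0.55, 0.60 and 0.46 in the three unequal cases). It shows the same pattern: equal rates cost events, and unequal rates move the ratio toward or away from 1 depending on which arm is unblinded more.

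**The case against.** Much of the case on the other side stands, and it limits the point.

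- **Not all deaths after unblinding are lost.** A reader might infer that they are. A subject with progression, confirmed relapse or treatment failure before unblinding already has an EFS event, and a later death changes nothing. If sites unblind mainly failing patients, this will be common. Affected subjects also stay in the analysis, as censored.
- **The link with prognosis is not documented.** Protocol 5.5.5.1 requires the date and reason of a blind break to be recorded but does not restrict the reasons. It is tempting to say that sites unblind patients who are doing badly; the documents do not say so. Nor does the SAP say why OS is exempt.
- **Bias is not established.** A reader might infer that the EFS hazard ratio is biased. In the illustration, equal unblinding left it unchanged.
- **The 6 to 13 deaths are not a ceiling.** The 63% is a whole-trial fraction. It is too low if unblinded subjects fare worse and too high if progression usually comes first.
- **EFS has little confirmatory weight.** It is last by default, 14th in SAP Table 7 and 16th in Table 8, and is tested only if everything above it succeeds.
- **The cutoff might be read at study level.** Table 4 uses the term that SAP 6.0 defines for the whole study. But SAP 10.1 explicitly replaces the cutoff for the individual subject, so the combined reading is the natural one. That two programmers could differ is itself a reason to settle the wording.

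The sponsor's unblinding after the final analysis results, in the current protocol, is a separate matter: the rule covers only premature breaks by sites before the cutoff.

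None of these points restores the censored deaths, and no other section does.

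**Conclusion.** The point holds as an inconsistency in the EFS rule. As written, a death after a premature site unblinding is censored when the subject was event-free at that time. This conflicts with the any-cause death component of EFS, with Table 4's treatment of deaths after new therapy, and with the protocol's definition.

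Its size cannot be derived from the documents. Informative censoring requires that unblinding be related to prognosis. A material shift in the hazard ratio requires, in addition, unequal rates between arms, and its direction depends on which arm is unblinded more. With equal rates the main cost is lost events. The primary analysis is untouched and the confirmatory impact is limited, so this is a correction that should be made rather than a threat to the trial's conclusion.

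**What to change.** In SAP 10.1 and 10.3.8:

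- apply the blind-break cutoff only to the assessed EFS components (progression, relapse, treatment failure);
- count any death on or before the study-level cutoff as an EFS event on the date of death, regardless of blind status;
- report the number of premature site unblindings by arm, with the recorded reasons;
- keep the present rule as a sensitivity analysis.

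The separate rule that censors at randomization any subject with no later disease assessment is left as it is.

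Protocol 1.1 states that the final analysis has been completed. For that analysis, run the corrected rule as a labelled EFS sensitivity analysis beside the reported result, and give the unblinding counts by arm.

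The cost is wording and one additional run. Death dates are already collected for OS, and the date and reason of each blind break are already recorded. One small drawback: progression between unblinding and death remains uncounted, so the event falls at the later date of death. Table 4 already accepts this after new therapy.

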10.2 Primary Efficacy Analysis

10.2.1 Overall Survival

Overall survival will be defined as the number of days from the date of randomization to the date of death. All events of death will be included, regardless of whether the event occurred while the subject was still taking study drug, or after the subject discontinued study drug. If a subject has not died, then the data will be censored at the date the subject was last known to be alive on or before the cutoff date. The date of the last known alive will be determined by selecting the last available date of the following study procedures for a subject: start date of adverse event, bone marrow collection, disease assessment, vital signs assessment, clinical laboratory collection, study drug administration, start date of concomitant medicine, transfusion procedure, survival follow-up, biospecimen sample collection, quality of life assessments, and performance status. All subjects in the full analysis set will be included in the analysis.

The distribution of overall survival will be estimated for each treatment arm using Kaplan-Meier methodology and compared between treatment arms using the log-rank test, stratified by AML status (de novo, secondary) and age ($18 - < 75, \geq 75$). The hazard ratio between treatment arms will be estimated using the Cox proportional hazards model, stratified by AML status (de novo, secondary) and age ($18 - < 75, \geq 75$).

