5.1.4 Post Treatment Follow-Up

After study treatment has ended and subjects have completed their Final Visit, subjects will be followed for overall survival, progressive disease and post-therapy disease status (if applicable). Survival information and post treatment follow up (i.e., the date and cause of death, all post treatment cancer therapies including transplantation, regimens, dates of initiation and completion, etc.) will be collected (e.g., via telephone calls and/or clinical visits) every 2 months until the end of the study. All subjects will be followed for

survival information (i.e., date and cause of death) unless the subject requests to be withdrawn specifically from this study survival follow-up; this request must be documented in the subject's medical record and signed by the Investigator. In such instances, sites may enter confirmation of death using source documentation from publically available records such as death certificates or funeral notices.

For subjects who had CR, CRi, MLFS, or PR at time of study drug discontinuation, hematology and disease assessments data will also be collected every 2 months (\pm 14 days) for 2 years after the last subject has been enrolled into the study.

For subjects who had RD, MR or PD at time of study drug discontinuation, survival phone calls will be conducted every 2 months (\pm 14 days) for 2 years after the last subject has been enrolled into the study.

30 Day Safety Follow-Up Visit

A Safety Follow-Up Visit should be performed for all subjects approximately 30 days following discontinuation of study drug and then as clinically appropriate for safety assessment. The subject will be followed until a satisfactory clinical resolution of the adverse event is achieved.

A Safety Follow-Up Visit does not need to be performed for subjects who had a Final Visit conducted $>$ 30 days after discontinuation of study drug and did not require additional adverse event follow-up. If the subject refuses or is unable to attend the Safety Follow-Up Visit, this should be noted in the subject's source documentation.

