4.2 Study Design and Plan

This is a Phase 3, randomized, double-blind, placebo controlled, multicenter study of venetoclax co-administered with LDAC versus LDAC in treatment naïve patients with acute myeloid leukemia who are ineligible for intensive induction chemotherapy sponsored by AbbVie. Subjects will be randomized to one of the two treatment arms in a 2:1 ratio, both of which will have treatment cycles of 28 days.

- Arm A: Venetoclax 600 mg orally QD on Days 1 – 28 plus LDAC 20 mg/m² SC QD on Days 1 – 10
- Arm B: Placebo for venetoclax 600 mg orally QD on Days 1 – 28 plus LDAC 20 mg/m² SC QD on Days 1 – 10

Approximately 210 subjects will be randomized to meet scientific and regulatory objectives without enrolling an undue number of subjects in alignment with ethical considerations.

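### OS survivors are censored at their last contact before the cutoff even when later shown to be alive, while deaths count up to the cutoff: survival is biased down in both arms, but the treatment comparison barely moves

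*SAP*

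**What the plan says.** SAP Section 10.2.1 takes in deaths on and off treatment: "All events of death will be included, regardless of whether the event occurred while the subject was still taking study drug". For a subject not known to have died, "the data will be censored at the date the subject was last known to be alive on or before the cutoff date". It adds: "The date of the last known alive will be determined by selecting the last available date of the following study procedures for a subject". The list is broad (adverse event start, laboratory and vital sign dates, dosing, transfusion, survival follow-up and others) but lacks the start date of post-treatment therapy. Protocol Section 8.1.4.1 also censors at the last date known alive, without mentioning a cutoff.

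SAP Section 6.0 sets the cutoff: "The data cutoff date for final analysis (FA) will be the projected date of the 133th death occurred in the full analysis set". The interim cutoff is set in the same way at the 100th death. SAP Section 10.1 has a final review of the eCRF data after the 133rd death and before extraction. Neither document plans a check of who is alive at the cutoff. SAP Section 10.6 lists an OS analysis that ignores the cutoff, but only as optional.

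Contact is denser on treatment than off it. Cycles last 28 days with a Day 1 visit (Protocol Appendix C), and a dosing date is itself proof of life. After treatment, Protocol Section 5.1.4 collects survival information "every 2 months until the end of the study". For subjects who withdraw from survival follow-up, "sites may enter confirmation of death using source documentation from publically available records".

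**The concern.** Take a subject off treatment who is contacted some weeks before the cutoff and next shortly after it. If the second contact reports a death before the cutoff, the death is an event on its true date. If it reports the subject alive, that information is discarded and the subject is censored at the first contact. The last interval before the cutoff thus contributes deaths without the matching survival time. Whether follow-up reaches the cutoff depends on the outcome, which is informative censoring. The public-record route works in the same direction, because it can add deaths but no survival time.

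OS is the primary endpoint. It can stop the trial at the interim (SAP Section 4.4) and it gates every secondary test (SAP Section 10.7). The interim is more exposed, because more subjects are then alive with short follow-up. Since the gap is longer off treatment, a difference between arms in time on treatment could also reach the comparison.

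**Working it through.** **1. The plan's own figure.** Inputs from SAP Section 4.3 and Table 1: medians 11 and 6 months, 2:1 allocation, two-sided 0.05, 90% power, 133 deaths, interim at 100.

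- Fixed design: (1.960 + 1.282)² / [(2/3)(1/3)(ln(6/11))²] = 10.51 / (0.2222 × 0.3674) ≈ 129 deaths.
- At 133 deaths, √(133 × 2/9) = 5.437. Power at the final critical value 2.012 is Φ(0.606 × 5.437 − 2.012) = Φ(1.283) = 0.900, or 0.904 with the interim look included.
- Lan-DeMets O'Brien-Fleming boundaries come out at 0.0097 and 0.0221 one-sided, against the plan's 0.010 and 0.022.

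The design reproduces. The hazard ratio that just reaches the final boundary is exp(−2.012/5.437) = 0.69.

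**2. Overstatement of hazards, by hand.** If the timing of contacts is uniform, the mean time lost per survivor is half the interval: 1 month off treatment, 14 days on. The crude hazard is multiplied by person-time / (person-time − time lost). Take every survivor as off treatment, which gives the largest loss, with the simulated mean number of survivors at the 133rd death (18-month accrual).

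- Design medians, venetoclax: 60.7 survivors, 79.3 deaths, person-time 79.3 × 11/0.693 ≈ 1,258 months. Factor 1,258/(1,258 − 61) = 1.051.
- Design medians, control: 16.3 survivors, 53.7 deaths, person-time 53.7 × 6/0.693 ≈ 465 months. Factor 465/(465 − 16) = 1.036.
- No effect, median 6 months in both arms: 51.2 and 25.6 survivors. Factors 769/(769 − 51) and 384/(384 − 26), both 1.07.

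Survivors still on treatment lose about half as much or less. Over the scenarios the overstatement is about 3% to 7%. Under the design medians it is larger in the venetoclax arm, which has more survivors.

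**3. Effect on the hazard ratio at the final analysis.** Simulation of 3,000 trials per scenario: 140 v 70 subjects, exponential survival and time on treatment, uniform accrual over 12 or 18 months, no loss to follow-up. Censoring at last contact is compared with censoring at the cutoff. All deaths to the cutoff are known except where stated.

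| Scenario (median months on treatment, venetoclax v control) | HR multiplied by |
|---|---|
| Design medians, 4 v 4 | 1.001 |
| Design medians, 5 v 2 | 0.997 |
| Design medians, 8 v 1.5 | 0.992 |
| No effect, equal time on treatment | 1.00 |
| No effect, longer on venetoclax | 0.98 to 0.995 |
| Deaths after the last contact not known at extraction | 1.000 to 1.001 |
| Unrealistic bound: no gap for any venetoclax survivor, 0 to 75 days for every control survivor | 0.951 (design), 0.915 to 0.944 (no effect) |

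Under the design medians, 0.545 becomes 0.545 × 0.992 = 0.541 to 0.545 × 1.001 = 0.546. Under no effect, a factor of 0.98 shifts z by −ln(0.98) × 5.437 = 0.11. The one-sided error at the final boundary then goes from 0.0221 to 1 − Φ(2.012 − 0.11) ≈ 0.029. Outside the bound, simulated rejection at a nominal one-sided 0.025 stayed near 0.025 to 0.034 (Monte Carlo standard error about 0.003).

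**4. Twelve-month survival and the interim.** With all deaths known and accrual over 12 to 20 months, 12-month Kaplan-Meier survival is understated by roughly 2 to 4 points at the interim and 1 to 2 at the final analysis, in both arms. The z shift is about zero with equal time on treatment (−0.012 under the design medians, slightly against venetoclax). It is +0.01 to +0.10 over the two looks with 5 v 2 months, and about +0.09 at the interim with 8 v 1.5. A shift of 0.10 at the interim boundary moves the error from 0.0097 to 1 − Φ(2.336 − 0.10) ≈ 0.013.

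**The case against.** The rule is ordinary and follows the protocol's definition. The list of dates is wide, and the optional analysis in SAP Section 10.6 would remove the truncation. The same 2-monthly contact reports both death and survival, so if extraction comes before the next contact, both are missing and the hazard ratio is unaffected. The public-record route covers only subjects who withdraw from survival follow-up, it is optional, and nothing indicates how many there would be. All of this stands as regards the comparison. It does not remove the downward bias in survival when deaths are known, and an optional analysis is not a safeguard.

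From the sparser contact off treatment, a reader might infer that the primary comparison is tilted toward venetoclax. That needs two things the documents do not state:

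- **Control survivors are more often off treatment at the cutoff.** Protocol Section 5.4.1 lists progression and failure to respond among the reasons to stop. The protocol cites a CR + CRi rate of about 11% with LDAC (Section 3.2) and 78% in 18 subjects on the combination (Section 3.0). A difference is plausible, but no expected time on treatment by arm is given, and SAP Section 9.0 only plans to summarise it.
- **Deaths after the last contact are known at extraction.** The cutoff is tied to the death count and a completeness review follows it, but the lag to extraction is not stated.

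Larger interim shifts, of +0.19 to +0.27, appeared only with 12 v 1.5 months on treatment, near-daily contact on treatment and no survival difference. An eight-fold difference in treatment time with equal survival is not a case the documents support.

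**Conclusion.** The asymmetry is real and lies in the SAP's wording. If deaths to the cutoff are known, it overstates hazards by about 3% to 7% in each arm at the final analysis and lowers reported 12-month survival by roughly 2 to 4 points at the interim and 1 to 2 points at the final analysis. The treatment comparison is nearly untouched. The hazard ratio shift is close to zero with equal time on treatment, and about 0.3% to 2% toward venetoclax at the final analysis only if control subjects leave treatment sooner. Against a boundary hazard ratio of about 0.69, that matters only for a borderline result. A claim of a built-in tilt or of materially inflated error is not supported.

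These sizes depend on the assumed exponential survival and time on treatment, uniform accrual and contact timing, and absence of loss to follow-up. The change should be made, but the validity of the primary test does not hang on it.

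**What to change.** - **SAP Section 10.2.1:** censor at the cutoff date any subject with a record showing him or her alive on or after the cutoff. Censor all other survivors at the last known alive date on or before it.
- **Alive-status check:** time the survival contacts that are already scheduled to fall at each OS cutoff and before extraction. Without this, the new rule works only in part, because survivors not yet contacted stay censored early.
- **SAP Section 10.6:** make the OS analysis without a cutoff a firm sensitivity analysis.
- **Minor extra:** add the start date of post-treatment therapy to the list of dates.

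Do not censor every survivor at the cutoff regardless of evidence, since unreported late deaths would then bias hazards downward. In particular, do not censor withdrawn subjects at the cutoff unless a complete public-record search has been made for all of them.

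The cost is a few lines of SAP text, one derivation and the scheduling of calls already planned. Protocol Section 1.1 reports that the final analysis has been completed. In that case the revised rule can be run on contacts already in the database and reported as a labelled sensitivity analysis.
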